#### **Participant Recruitment**

Patients will be recruited from [name] clinic after being selected as candidates for total knee arthroplasty. [name] and the study team will provide patients with information regarding the study and patients will be allowed to volunteer to participate.

## **Randomization**

Prior to surgery in the clinic visit, patients will be given the The Pain Catastrophizing Scale, PCS short form. Based on the results of surveys, we will only include patients with Mild or Moderate anxiety towards pain. Eligible patients will be asked if they would enroll in the study. The survey will allow the opportunity to find a homogenized patients group for treatment and control groups.

Enrolled patients will be randomly selected into `IFC treatment` or `Control` groups after their surgery. This will enable us to eliminate any possible surgical bias.

We will use block randomization for this study: the surgeon and study group will not interfere in the randomization process to eliminate possible bias. Participants will be randomized in a 1:1 ratio (treatment:placebo). A block randomization scheme with a block size of 6 will be generated and maintained by the study statistician. The statistician will provide the sites with a set of randomization envelopes to be used in the study clinics. The randomization envelopes will be stored by the study coordinators in a locked cabinet. Study staff, not including the investigator who will perform clinical evaluations after surgery, will assign these envelopes in sequential order, by envelope number, to eligible participants. Each randomization envelope will include study treatment arm randomization assignment. Assignment of the randomization envelope is considered the effective act of participant enrollment/randomization.

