# Study Design:

It will be a prospective, randomized, single-blinded study. The study device will be used for only 2 days during the post-surgery hospital stay. The patients will be followed until their 6 weeks post-op office visit. We aim to finalize the study in 6 months.

Before enrollment into the study: During their pre-operative visit, patients will fill out a short questionnaire (The Pain Catastrophizing Scale, PCS short form) to assess their eligibility for the treatment and create a homogenized group of patients. Inclusion criteria is detailed below. 50 patients who are eligible for the study will be enrolled by written consent. Informed written consent will be obtained by PI ([name]) and the health care professional team ([name] and [name],PA ) during pre-operation office visit.

Once the patient volunteers to enroll to the study, we will establish their patient-specific intensity during their pre-op office visit. We will plan to have patient establish their correct and comfortable intensity before their surgery. The device comes in a carrying case with all the set supplies. At the time of placement, a health care provider will place the pre-packaged sterile electrode roughly 7-10 cm above and below the knee for testing or just above and below the

dressing during on the operated knee. Each set of electrodes will then be connected via a lead wire to the stimulation device.

Establishing the correct and comfortable intensity before operation will be as follows: The stimulation device which has a large power button will be turned on but provide no initial signal intensity. The patient will then be instructed to use the "plus" arrow on the device to slowly increase the signal intensity. The goal is to reach a point of intensity that feels strong but comfortable. The best method is to continue to increase to the point where it becomes slightly uncomfortable and the patient may experience some muscle fasciculations. Once that point is reached, decrease the intensity slightly and then use that intensity for their treatment. This patient specific intensity will be recorded and used for the IFC treatment.

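### The protocol prints a single fixed block size of 6, so someone who knows it and the earlier allocations in a block would know about 24% of the 50 planned allocations in advance

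*Combined protocol and SAP*

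**What the plan says.** The Randomization section gives one fixed value, "A block randomization scheme with a block size of 6", and a 1:1 ratio. The study statistician generates and keeps the list. No stratification factor and no variation in block size is described. Study Population names one surgeon, and the Monitoring paragraph says there is one site, so the trial runs on one sequence.

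The same section contains several safeguards:
- The envelopes are kept locked up, and staff "will assign these envelopes in sequential order, by envelope number, to eligible participants".
- Those who do so are "Study staff, not including the investigator who will perform clinical evaluations after surgery".
- It adds that "the surgeon and study group will not interfere in the randomization process to eliminate possible bias".
- Allocation takes place after surgery, and consent is obtained at the pre-operative visit.

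Two further statements bear on the point. Study Design says "It will be a prospective, randomized, single-blinded study" without saying who is blinded, and it describes the placebo devices as a separate set. The Randomization section ends with "Assignment of the randomization envelope is considered the effective act of participant enrollment/randomization". The documents do not say that the envelopes are opaque or sealed, or that the block size is withheld from clinical staff.

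**The concern.** When the block size is fixed and known, anyone who has followed the allocations in a block can work out what is left. Once three patients in a block have gone to one arm, the remaining arms in that block are determined. The block size stands in a protocol that the study team reads, and the staff who assign envelopes can plausibly see or remember earlier arms.

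The stake is selection at the moment of allocation. Because the envelope counts as the act of enrolment, there is an interval after surgery in which a consented patient is not yet randomised. Someone who foresees the next arm and has seen how surgery went could hold a patient back or change the order of two patients. A patient held back would not appear among the randomised. Foreknowledge can also colour staff expectation and behaviour. The primary outcome is pain medication use over the next 24 and 48 hours, and with 25 patients per arm a few steered allocations could matter.

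**Working it through.** **The plan's own figure.** The protocol gives no figure for predictability. Its one calculated figure is the sample size, used here only to price imbalance. With a difference of 0.30 × 84.2 = 25.26 mg, SD 44.7, two-sided 0.05 and 80% power, the t-test calculation gives 50.1 per group. This reproduces the stated 50.

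**Inputs.** Block size 6 and ratio 1:1, so 3 + 3 per block (Randomization). Planned enrolment 50, 25 per group (Study Design; Power/sample size). Assumption: the observer knows the block size and every earlier arm in the current block.

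**1. Certainty within a block.** There are C(6,3) = 20 equally likely blocks. An allocation is certain once one arm has been used three times. Of the 20 blocks, 12 end with one certain allocation, 6 with two and 2 with three:

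(12×1 + 6×2 + 2×3) / 20 = 30/20 = 1.5 per block, and 1.5/6 = 25.0%.

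The closed form 2m/(m+1) with m = 3 also gives 1.5.

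| Position in block | 1 | 2 | 3 | 4 | 5 | 6 |
|---|---|---|---|---|---|---|
| Probability that the arm is certain | 0 | 0 | 0 | 0.10 | 0.40 | 1.00 |
| Probability that the best guess is right | 0.5 | 0.6 | 0.6 | 0.7 | 0.7 | 1.0 |

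**2. Certainty at the planned size.** 50 = 8 full blocks + 2 patients. Expected certain allocations: 8 × 1.5 + 0 = 12.0, and 12/50 = 24.0%.

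**3. Best guess under fixed blocks of 6.** The bottom row sums to 4.1, so 4.1/6 = 68.3% per full block. At 50 patients: (8 × 4.1 + 0.5 + 0.6)/50 = 33.9/50 = 67.8%.

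**4. Randomly varied sizes.** Lists of 50 were simulated with block sizes drawn at random, for an observer who knows the set of sizes and all past allocations.

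| Scheme | Certain |
|---|---|
| Fixed 6 | 24% |
| Random 4 or 6 | about 5.5% |
| Random 4, 6 or 8 | about 2.5% |

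For random 4, 6 or 8 that is 0.025 × 50, or about one patient instead of 12. The best-guess rate is about 68%, the same as in step 3. Choosing a different fixed size does much less: 33.3% certain per block for size 4 and 20% for size 8.

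**5. Imbalance.** With fixed blocks of 6, patient 50 is the second in a block. Both of those patients fall in one arm with probability 2 × (3/6) × (2/5) = 0.40, so 26:24 already occurs in about 40% of lists. With sizes 4, 6 and 8 the worst split is 27:23. It needs a block of 8 to start after patient 46 and to open with four patients in one arm. Blocks average 6 and start only after even counts, so this has probability of about (2/6) × (1/3) × (2/70) = 0.3%. Power for the protocol's difference is 0.499 at 25:25 and 0.497 at 27:23.

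**The case against.** The strongest reply is that the route to harm is narrow. Consent, eligibility screening and surgery are complete before any envelope is assigned, so foreknowledge cannot affect who is asked to join. The evaluator does not assign envelopes, and the envelopes are used in numbered order. A consented patient who never received an envelope would still leave a consent form and a recorded pre-operative intensity. Delay is limited too, because the sessions run twice daily for two days within a stay of 48 to 72 hours. All of this stands. It confines the risk to withholding a patient, swapping patients operated on close together, and staff expectation. It does not close the gap, because none of these safeguards stops deduction from a printed block size and known arms.

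A second reply is that varying the block sizes leaves the best-guess rate unchanged for an observer who knows the set of sizes. That is correct, so the benefit should be described as the removal of near-certainty only.

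A reader might also infer that staff are unblinded and that one allocation in four is therefore known to them. The documents do not support this. They say only that the trial is single-blinded. They do not say who knows the arms, whether the two sets of devices can be told apart by eye, or whether anyone follows the sequence. Knowledge of earlier arms is plausible for those who assign envelopes, but it is an inference.

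**Conclusion.** The point holds as a minor weakness of allocation concealment. Under the stated scheme, a person who knows the block size and all earlier arms in a block would know 12 of 50 allocations in advance (24%; 25% per full block), always including the sixth. The figure depends on that knowledge, and also on the absence of strata, of which the documents describe none.

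It would go too far to say that the scheme defeats the protocol's aim of eliminating bias. Allocating after surgery still protects the operation itself from knowledge of the arm, and the other safeguards remain. The documents give no basis for estimating a bias in opioid use, and none is claimed here.

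**What to change.** - Have the statistician generate the list with randomly varied block sizes, for example 4, 6 and 8.
- Remove the block size from the protocol, state there only that sizes vary, and keep them in a document that only the statistician holds.
- State that the envelopes are opaque and sealed. Numbered order and allocation after surgery are already specified and can stay as they are.

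The cost is one line in the randomisation program and a sentence or two in the protocol. The downside is a 27:23 split in under 1% of lists, with power of 0.497 instead of 0.499.

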# **Risk/Benefit**

#### Risks

i. Skin irritation: four prior studies mention skin irritation or thermal damage with IFC use [10-13]. Two of these studies were using IFC materials from older generation products [10, 11]. In one case report by Ford et al. [13] using IFC after total knee arthroplasty, the issues was theorized to be due to placement near the infrapatellar branch of the saphenous nerve which can be frequently insensate after total knee arthroplasty.

1. In order to limit risk, leads will be placed above and below the dressing to avoid skin irritation due to insensate skin.

2. Patient determined settings will be recorded during pre-operative visit prior to anesthesia local nerve block/spinal injection to prevent patients with slightly diminished sensation post-operatively from using too high a setting.

Loss of concentration, drowsiness, decreased alertness- One case report described a patient having temporary symptoms of loss of concentration, drowsiness, decreased alertness and gait disturbances for 4-5hours after IFC treatment. The reason was theorized to be opioid like reaction due to endogenous opioid release [14]. Although a rare risk, patients will be monitored in the hospital setting by medical staff throughout their admission and use of IFC treatment.

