# **Study Population**

a. The study population will be adult patients older than 18 with severe knee osteoarthritis that have failed non-operative conservative therapy and now require total knee arthroplasty. All patients will undergo unilateral primary total knee arthroplasty with the Zimmer Persona prosthesis performed by [name].

Pre-operative clearance will be done by the Montefiore Geriatrics team prior to day of surgery. Inclusion criteria: Adult patients with knee osteoarthritis who have failed conservative therapy and undergoing elected TKA.

Exclusion criteria:

i. <18 years old

ii. Any patient with pacemaker or any electrical stimulator device

- iii. Significant baseline deformity (flexion contracture)
- iv. Patient with clinically diagnosed fibromyalgia?
- v. Patients without capacity to consent for the study
- vi. Patients not able to have local nerve block or spinal anesthesia
- vii. Patients with prior opioid use

viii. Patient who is categorized to have `Severe` fear and anxiety responses to pain, according to the PCS survey.

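### No exclusion or check covers sensory loss already present in the operative leg, although the IFC intensity is set before surgery mainly by what the patient feels

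*Combined protocol and SAP*

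**What the plan says.** **Hazard.** Risk/Benefit, Risks, item i, reports skin irritation or thermal damage in four earlier publications on IFC. For one case after knee arthroplasty, it relates the injury to electrode placement near a nerve branch "which can be frequently insensate after total knee arthroplasty".

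**Mitigations.** The same item gives two. First, "leads will be placed above and below the dressing to avoid skin irritation due to insensate skin". Second, the setting is recorded "prior to anesthesia local nerve block/spinal injection to prevent patients with slightly diminished sensation post-operatively from using too high a setting".

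**How the setting is found.** Under Study Design, a provider is to "place the pre-packaged sterile electrode roughly 7-10 cm above and below the knee for testing or just above and below the" dressing. The patient then raises the intensity: "The best method is to continue to increase to the point where it becomes slightly uncomfortable and the patient may experience some muscle fasciculations". It is then lowered slightly, and "This patient specific intensity will be recorded and used for the IFC treatment".

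**Exposure.** The IFC arm is treated twice daily for two days. Each session ends automatically at 30 minutes, and the device scale runs to 100. The patient may sleep during a session. The adhesive pads may stay on between sessions or be taken off and replaced.

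**Eligibility.** Study Population lists eight exclusions. The only one aimed at the safety of electrical stimulation is "Any patient with pacemaker or any electrical stimulator device".

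**Monitoring.** The Risks section says that "patients will be monitored in the hospital setting by medical staff throughout their admission and use of IFC treatment". That sentence belongs to the paragraph on drowsiness and reduced alertness.

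**The concern.** The plan accepts that reduced sensation can lead to too high a setting, and it guards against the reduction that surgery or anaesthesia would cause. It does not consider a patient whose sensation at the electrode sites is reduced before either. For that patient, setting the intensity before the block gives no protection, because the reference value comes from a leg that already under-reports discomfort.

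What is at stake is the safety of individual participants in the IFC arm: a possible skin or thermal injury from a setting that is too high and is used again at each session. The primary outcome, the power and the planned analysis are not affected.

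**Working it through.** The point rests on the text. The plan gives no figure for it to reproduce, so the relevant sections are set side by side.

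**1. Does any eligibility criterion cover leg sensation?** The eight exclusions in Study Population are:

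| Exclusion | Covers sensory loss in the leg? |
|---|---|
| i. Under 18 | No |
| ii. Pacemaker or stimulator | No; electrical safety of an implanted device |
| iii. Flexion contracture | No |
| iv. Fibromyalgia | No; a pain condition |
| v. No capacity to consent | No |
| vi. Unable to have a nerve block or spinal | Not directly; may remove some patients with neurological disease |
| vii. Prior opioid use | No |
| viii. Severe category on the pain catastrophizing survey | No |

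The inclusion criterion does not ask for intact sensation. Clearance by the Geriatrics team is required, but no sensory test is described as part of it.

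**2. What does each mitigation cover?**

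| Mitigation (Risks, item i) | Cause of numbness addressed | Works if sensation was already reduced? |
|---|---|---|
| Leads above and below the dressing | Surgery | Only if the loss does not extend to those sites |
| Setting recorded before block or spinal | Anaesthesia | No |

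**3. How far does the setting depend on feeling?** Study Design aims for an intensity that is strong yet comfortable, found by going just past comfort and then stepping back. Muscle fasciculation does not depend on skin sensation, but it is described as something that may occur, not as a point at which to stop. The only ceiling stated is the device maximum of 100. The setting therefore depends mainly, though not wholly, on sensation.

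**4. Exposure at that setting.** Sessions per IFC patient = 2 per day × 2 days = 4. Total time = 4 × 30 minutes = 120 minutes. This is the schedule for every IFC patient; it is not a measure of risk.

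**5. Can the harm be sized?** No. The documents give no prevalence of sensory loss among candidates, no injury rate, and no intensity on the 0 to 100 scale that is known to be harmful. With 25 patients planned for the IFC arm, the number affected could be zero.

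**The case against.** The strongest reply is that the residual risk is small and already reduced in several ways:

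- The intensity is lowered from the uncomfortable point before it is recorded.
- Fasciculations may give a visible cue.
- Sessions stop at 30 minutes.
- Pads may be removed between sessions.
- Staff record range of motion and thigh circumference daily, so the leg is handled close to the electrode region.
- Geriatrics clears each patient before surgery, and exclusion vi may remove some patients with neurological disease.
- Patients are in hospital under observation while the device is used.

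All of this stands as mitigation. None of it is a sensory test, and none specifies looking at the skin under the electrodes. Because patients may sleep during treatment and pads may stay on, neither patient feedback nor a view of the skin is assured.

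A reader might infer from the reference list, where reference 11 reports third-degree burns with interferential current, that patients with prior sensory loss are known to be burned by this treatment. The documents do not support that. The Risks section says that reference 11 involved older-generation products. The case in reference 13, whose title reports a full-thickness burn, is attributed to numbness after arthroplasty, which lead placement is meant to address. No injury in the documents is linked to sensory loss that preceded surgery.

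**Conclusion.** The gap is real on the text. Followed as written, the plan can admit a patient for whom its own set-before-the-block safeguard does not work, and no other step is designed to detect this.

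The conclusion rests on two things: the plan's own link between diminished sensation and an excessive setting, and the assumption that some candidates for knee arthroplasty may have reduced sensation at the electrode sites before surgery. The documents neither confirm nor exclude the second.

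The size is unknown. The harm is possible and undocumented, and the number affected may be zero. It would go too far to say that the plan ignores numb skin, that it has no safeguards, or that injuries should be expected. The point warrants a modest, inexpensive safety improvement.

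**What to change.** Add an exclusion to Study Population: known peripheral neuropathy, or clinically evident loss of sensation at the planned electrode sites on the operative leg.

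Confirm it with a brief light-touch check at the pre-operative visit, before the intensity is set, by the provider who places the electrodes. Check both positions given in Study Design: the test sites about 7–10 cm above and below the knee, and the expected sites just above and below the dressing.

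Exclusion is preferable to the alternatives. An intensity cap would need a safe threshold that the documents do not give. Skin inspection alone finds an injury only after it has begun.

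Randomisation takes place after surgery, and the Randomization section treats assignment of the envelope as the effective act of enrolment. Patients who fail the check are therefore screen failures and not post-randomisation exclusions, even if they have already signed consent. State that they are replaced, so that the planned 25 per group is kept.

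Cost: one added criterion and a short check at a visit already planned, with no extra staff. The downside is a few screen failures, whose number cannot be estimated from the documents, and slightly narrower generalisability.

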#### **Benefits**

Improved post-operative outcomes (pain control, range of motion, edema) can result in: faster return to activities of daily living, decreased time immobilized, reduced risk of DVT, improved quality of life, decreased need for opioid medication post-operatively, decreased risk of opioid dependence, shortened hospital stay.

# Data and Safety Monitoring

# 1. Data and Safety Monitoring Board

This study will be monitored by a Data and Safety Monitoring Board. The Data Safety Monitoring Board (DSMB) will be responsible for oversight of data and safety. The DSMB will be composed of three experts in orthopaedic surgery and clinical trial methodology, [name], MD., [name], MD. and [name], PA. The DSMB members will be independent of all those participating in the study.

The DSMB will review data on adverse events, data quality, and subject recruitment every 6 months and/or at the end of study.

The DSMB will prepare meeting minutes and make recommendations about study conduct to the Principal Investigator.

The research team will meet with DSMB and review data on adverse events, data quality, and subject recruitment every three months until the study is completed. If there is any serious adverse event, it will be reported to the Sponsor and to IRB within 5 business days. Similarly, minor adverse events will be reported to the Sponsor within 5 business days and those will be included in the annual progress report or when the study is closed.

